2. Patients with Rheumatoid Arthritis, Osteoarthritis, or Inflammatory Arthritis undergoing **primary total hip replacement surgery, primary total knee replacement surgery, primary total elbow replacement surgery or primary total shoulder replacement surgery**

3. Satisfy ACR/EULAR 2010 classification criteria and/or the 1987 RA criteria (see below) and be diagnosed with RA (unless IA patient or OA control).

Rheumatoid arthritis 1987 criteria:

1. morning stiffness in and around joints lasting at least 1 hour before maximal improvement;
2. soft tissue swelling (arthritis) of 3 or more joint areas observed by a physician;
3. swelling (arthritis) of the proximal interphalangeal, metacarpophalangeal, or wrist joints;
4. symmetric swelling (arthritis);
5. rheumatoid nodules;
6. the presence of rheumatoid factor; and
7. radiographic erosions and/or periarticular osteopenia in hand and/or wrist joints.

*Criteria 1 through 4 must have been present for at least 6 weeks. Rheumatoid arthritis is defined by the presence of 4 or more criteria, and no further qualifications (classic, definite, or probable) or list of exclusions are required.

ACR/EULAR 2010 criteria for the classification of RA:

Table 3. The 2010 American College of Rheumatology/European League Against Rheumatism classification criteria for rheumatoid arthritis

Target population (Who should be tested?): Patients who

- 1) have at least 1 joint with definite clinical synovitis (swelling)*
- 2) with the synovitis not better explained by another disease

Classification criteria for RA (score-based algorithm: add score of categories A-D;

a score of $\geq 6/10$ is needed for classification of a patient as having definite RA

Score

A. Joint involvement

0	1 large joint	
	2-10 large joints	1
	1-3 small joints (with or without involvement of large joints)	2
	4-10 small joints (with or without involvement of large joints)	3
	>10 joints (at least 1 small joint)	5

B. Serology (at least 1 test result is needed for classification)

0	Negative RF and negative ACPA	
	Low-positive RF or low-positive ACPA	2
3	High-positive RF or high-positive ACPA	

C. Acute-phase reactants (at least 1 test result is needed for classification)

0	Normal CRP and normal ESR
1	Abnormal CRP or abnormal ESR

D. Duration of symptoms

0	< 6 weeks
1	≥ 6 weeks

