They will receive a Study Overview Sheet (see attached) either in the office, in the mail, or on the day of surgery. They will have the opportunity to discuss any questions with the research assistant/ research team member who will ensure they meet study criteria (see screening sheet). In addition, patients may be identified and recruited from the Total Joint Replacement Patient Education Class by the research assistant. Finally, research assistants may use PS Reporter, MMF, or Clinstar to identify patients before their pre-surgical screening visit, or prior to their surgical procedure. We will request an IRB approved Waiver of HIPAA Authorization.

6.0 * Please select enrollment type from following drop down list:

Over Course of Study

[Help](#)

ID: 2014-233

View: 2.3 Target Enrollment

[Help](#)

Target Enrollment

- 1.0 * What is the maximum number of subject you plan to enroll in this study at HSS?(Please enter a number)
200
- 2.0 If this is a multi-center study, indicate the projected total subject accrual across all sites.

[Help](#)

ID: 2014-233

View: 2.35 Patient Subjects

[Help](#)

Patients

1.0 Please check the box(es) below that best reflect how patients will be identified and recruited for participation.

How subjects will be identified

- ☒ Potential subjects will be identified after a review of medical records of patients under the care of one or more of the study investigators
- ☒ Medical records and/or other Institution sources (databases, registries, billing records, pathology reports, admission logs) will be reviewed to identify potential participants. May involve access of records by individuals not involved in the patient's care.
- ☒ Potential subjects will be identified by their treating physicians and referred to the researchers. Patients' private and identifiable information will not be shared prior to receiving permission from the patient to do so.
- ☐ Potential subjects will be identified from a registry of individuals interested in research opportunities.
- ☐ Subjects will roll-over from another research study.
- ☐ Potential subjects will self-refer in response to advertisements.

ID: 2014-233

View: 2.6 Interventions and Observations

[Help](#)

Interventions and Observations

1.0 Be specific and describe the Interventions or Observations that will be part of this research project. Include a detailed description of the treatment arms, if applicable.

Clinical Data:

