- Based on data quoted above we have chosen a conservative estimate of flare as 26%.

Ho: within 6 weeks we have a flare rate for RA patients=0.26

Ha: within 6 weeks the flare rate is different from 0.26(=0.1 0.15 0.2)

Power Analysis of One Proportion

Numeric Results for testing H0: P = P0 versus H1: P <> P0

Test Statistic: Exact Test

		Proportion Given H0	Proportion Given H1	Target	
Actual		(P0)	(P1)	Alpha	
Power Alpha	N Beta				
0.8143 0.1857	47	0.2600	0.1000	0.0500	0.0445
0.8036 0.1964	109	0.2600	0.1500	0.0500	0.0387
0.8017 0.1983	394	0.2600	0.2000	0.0500	0.0445

Report Definitions

Power is the probability of rejecting a false null hypothesis. It should be close to one.

N is the size of the sample drawn from the population.

To conserve resources, it should be small.

Alpha is the probability of rejecting a true null hypothesis. It should be small.

Beta is the probability of accepting a false null hypothesis. It should be small.

P0 is the value of the population proportion under the null hypothesis.

P1 is the value of the population proportion under the alternative hypothesis.

Summary Statements

A sample size of 47 achieves 81% power to detect a difference (P1-P0) of -0.1600 using a

two-sided binomial test. The target significance level is 0.0500. The actual significance level

achieved by this test is 0.0445. These results assume that the population proportion under the

null hypothesis is 0.2600.

Power Analysis of One Proportion

Chart Section

We are estimating the rate of the flare rate in RA post-arthroplasty based on previous data. However, if our estimates are wrong, we may be grossly underpowered. Therefore, an interim analysis is planned, when we have collected 25 RA patients to ensure we are adequately powered to detect the primary outcome of flare as previously defined.

- Alpha level: 0.05
- Beta or power level: 0.8 (80%)
- Primary outcome variable estimate (mean +/- s.d. for continuous outcome, frequency/percentage for categorical variable):

The primary outcome is rate of RA flare within 6 weeks of surgery. Since it's a rate, no mean and s.d. are available.

- Number of groups being compared (use 1 for paired analysis within the same subjects):

2 groups: RA – Flare vs. Non-Flare group for secondary outcome.

- Effect size or change expected between groups:

The expected effect size between the flare and non-flare group is 16%, but the interim analysis will be performed after we collect 50 patients.

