- Resulting number per group:

47 with effect size 16% (0.25-0.10) overall.

109 with effect size 11% (0.25-0.15) overall.

394 with effect size 6% (0.25-0.20) overall.

- Total sample size required:

47 patients will provide an adequate sample size to evaluate the primary outcome and enable explorations for the secondary outcomes in this study. It is anticipated that 20% will drop out of the study thus we will need to recruit 57 patients to this study to adequately study the primary and secondary outcomes in this study.

References

Fleiss, J. L., Levin, B., Paik, M.C. 2003. Statistical Methods for Rates and Proportions. Third Edition. John

Wiley & Sons. New York.

Lachin, John M. 2000. Biostatistical Methods. John Wiley & Sons. New York.

Edition. Blackwell Science. Malden, Mass.

Zar, Jerrold H. 1984. Biostatistical Analysis (Second Edition). Prentice-Hall. Englewood Cliffs, New Jersey.

3.0

Data Analysis: describe how the primary outcome will be analyzed and what types of statistical calculations will be used. Do the same for each secondary outcome. Reiterate briefly the main analysis to be done, which groups, which variables, possible confounders. Address how possible confounders will be identified and handled in analysis:

For the Primary Outcome:

Descriptive statistics (rates and proportions, frequency distributions, means, medians, standard deviations and inter-quartile ranges) will be used to describe the baseline data. The two-tailed unpaired Student's t test, or Kruskal-Wallis tests will be performed to evaluate differences in continuous variables between groups (Flare vs. non-Flare group), depending on the distribution of the data, and the Scheffe or Bonferroni multiple comparisons test will be used for multiple comparisons. Chi-Square or Fisher's exact test will be utilized here to compare proportions between groups. Logistic regression will be performed for the HOOS and KOOS score to adjust for potential confounders and effect modifiers.

All secondary outcomes are exploratory.

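### The 81% power is for 47 evaluable RA patients, but the recruitment target of 57 is not labelled RA and does not deliver that power on either reading

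*Combined protocol and SAP*

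**What the plan says.** Section 2.11.1 (Sample Size) sets the null hypothesis for one diagnosis: "Ho: within 6 weeks we have a flare rate for RA patients=0.26". The alternatives are 0.10, 0.15 and 0.20. The method is given as "Test Statistic: Exact Test", with a two-sided target level of 0.05, and the summary of power begins "A sample size of 47 achieves 81% power to detect a difference (P1-P0) of -0.1600 using a".

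Under the total sample size, the same section takes 47 as adequate for the primary outcome and continues: "It is anticipated that 20% will drop out of the study thus we will need to recruit 57 patients to this study". No diagnosis is attached to the 57.

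The inclusion criteria in section 2.3 (Recruitment) admit "Patients with Rheumatoid Arthritis, Osteoarthritis, or Inflammatory Arthritis undergoing" primary hip, knee, elbow or shoulder replacement. Section 2.8 names OA patients as a comparator group. Section 2.6 gives the weekly flare questions to RA patients only.

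Section 2.3 (Target Enrollment) asks "What is the maximum number of subject you plan to enroll in this study at HSS", and the answer is 200, with no split by diagnosis. The documents give no RA quota, no OA or IA target and no expected mix.

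**The concern.** Only RA patients can contribute to an RA flare rate, so the power and precision of the primary result depend on the RA count alone. The plan justifies its size with 81% power at 47 evaluable RA patients, but neither enrolment figure is expressed in RA patients. Section 2.11.1 is also uneven in its labels: it sets the interim look at 25 RA patients in one place and at 50 patients, without a diagnosis, in another. A reader therefore cannot rely on the word patients meaning RA there.

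A team that recruited to 57 as written could stop short of the number the power claim needs. The plan itself warns that it may be badly underpowered if its assumptions are wrong, so the figure should be secure on its own terms.

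**Working it through.** **Inputs.** From 2.11.1: P0 = 0.26, P1 = 0.10, two-sided alpha 0.05, exact one-sample binomial test, N = 47, dropout 20%, target 57. From 2.3: maximum 200. The RA share is not given, so any value used for it below is an assumption.

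**Reproducing the plan.** Take an equal-tailed exact test: reject if flares ≤ L or ≥ U, where P(X ≤ L) and P(X ≥ U) are each at most 0.025 under P0. Power is the same rejection probability under P1.

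| N | P1 | Reject if | Actual alpha | Power | Printed power |
|---|---|---|---|---|---|
| 47 | 0.10 | ≤6 or ≥19 | 0.0445 | 0.8143 | 0.8143 |
| 109 | 0.15 | ≤19 or ≥39 | 0.0387 | 0.8036 | 0.8036 |
| 394 | 0.20 | ≤85 or ≥121 | 0.0445 | 0.8017 | 0.8017 |

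All three printed rows are reproduced, so the same test can be used at other sizes.

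**Where 57 comes from.** 47 × 1.2 = 56.4, rounded up to 57. To keep 47 after 20% dropout, the calculation is 47 / (1 − 0.20) = 58.75, so 59. Check: 57 × 0.8 = 45.6 and 59 × 0.8 = 47.2.

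**Reading A: all 57 are RA.** P1 = 0.10:

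| Evaluable | Reject if | Actual alpha | Power |
|---|---|---|---|
| 45 | ≤5 or ≥19 | 0.0256 | 70.8% |
| 46 | ≤5 or ≥19 | 0.0272 | 69.0% |
| 47 | ≤6 or ≥19 | 0.0445 | 81.4% |

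The drop arises because P(X ≤ 6) under P0 is 0.0273 at n = 46, above 0.025, and 0.0228 at n = 47. The lower limit therefore moves from 6 to 5.

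**Reading B: OA or IA patients count toward the 57.** Evaluable RA = 57 × share × 0.8, rounded down; shares assumed:

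| RA share | Evaluable RA | Power at 0.10 |
|---|---|---|
| 75% | 34 | 55.4% |
| 67% | 30 | 41.1% |
| 50% | 22 | 33.9% |

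Exact power moves in steps, so single rows should not be over-read. An 80% share gives 57 × 0.8 × 0.8 = 36.5 evaluable, and power is 50.9% at 36 but 69.0% at 37.

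**The ceiling of 200.** With 20% dropout, 47 evaluable RA patients need 59 RA enrolled, and 59 / 200 = 29.5%. If 200 are enrolled, a 25% share gives 40 evaluable and 62.9% power; 29.5% gives 47 and 81.4%; 50% gives 80 and 94.6%.

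**Precision.** Half-width of the 95% interval at a 26% rate = 1.96 × √(0.26 × 0.74 / n): 12.5 points at n = 47, 12.8 at n = 45, 15.7 at n = 30.

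**The case against.** The best defence is that 57 plainly means RA patients. It is computed from 47, the 47 belongs to an RA-only hypothesis, and nothing in the text says OA or IA patients count toward it. That is the more natural reading, and the documents do not establish that 57 is a mixed total. It does not rescue the figure, though, because 57 RA patients at 20% dropout still leave fewer than 47.

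A second defence is that this last shortfall is one or two patients and the fall in power is partly a feature of the discrete test. That is fair. The interval half-width barely changes, and 47 sits at a local peak. The plan nevertheless chose an exact test and quotes its power at 47, so the figure at 45 or 46 is the one its own recruitment target supports.

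A reader might also infer that the maximum of 200 fails to deliver the RA number, or that it competes with 57 as a second sample size. The documents do not support this: 200 is a cap, it can coexist with an RA target, and it is ample once the RA share reaches about 29.5%. What stands is only that it guarantees no RA number.

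**Conclusion.** The recruitment target of 57 does not deliver the printed 81% power. If all 57 are RA, power for 0.26 against 0.10 is about 69 to 71%, below the plan's 80% target; this uses only the plan's own test and dropout rate. If the 57 includes other diagnoses, power is lower still, but the size of that loss depends on an RA share the documents do not give, so 41% at two-thirds RA is an illustration. The 200 neither secures nor rules out 47 evaluable RA patients.

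A reader might go further and infer that the final number could be chosen after seeing the accumulating flare rate. No section ties the final number to the observed rate. The planned interim look at adequacy of power comes closest, but it does not say this, so the inference is not part of the point.

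This is an error in a figure the study relies on for its primary outcome, and it can be corrected cheaply. The absence of an RA, OA and IA split of the 200 is missing detail only.

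**What to change.** In section 2.11.1:

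- State the target as 47 RA patients with an evaluable 6-week flare outcome, which needs 59 RA patients enrolled at 20% dropout. Alternatively, keep 57 and label it RA, and restate power as about 70%.
- State that OA and IA patients do not count toward this target.
- Fix the RA number at which the primary rate is analysed, and give the exact power and the interval half-width at that number (81.4% and 12.5 points at 47).

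It would also help to show in section 2.3 how the 200 divides among RA, OA and IA, so that the RA target is visibly within it.

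The cost is protocol wording. Moving from 57 to 59 adds two RA patients, within the 200 already requested.

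### Recruiting 57 with 20% dropout leaves 45 to 46 evaluable RA patients, where the plan's own exact test has about 70% power rather than 81%; the 16-point effect is also mislabelled and its brackets do not compute

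*Combined protocol and SAP*

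**What the plan says.** All of this stands in View 2.11.1, Sample Size, item 2.0, of the combined protocol and SAP.

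- Hypotheses: "Ho: within 6 weeks we have a flare rate for RA patients=0.26" against "Ha: within 6 weeks the flare rate is different from 0.26(=0.1 0.15 0.2").
- Test: the power table is headed "Test Statistic: Exact Test", and the summary statement calls it two-sided. "The target significance level is 0.0500".
- Result: "A sample size of 47 achieves 81% power to detect a difference (P1-P0) of -0.1600 using a" two-sided binomial test, with an actual alpha of 0.0445. The target power is 80%.
- Effect size entry: "The expected effect size between the flare and non-flare group is 16" per cent.
- Entry under the number per group: "47 with effect size 16% (0.25-0.10) overall". The two lines after it give 11% as 0.25-0.15 and 6% as 0.25-0.20.
- Total: 47 patients are said to suffice. Then: "It is anticipated that 20% will drop out of the study thus we will need to recruit 57 patients to this study", which is said to be adequate for both the primary and the secondary outcomes.

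Item 3.0 of the same section declares all secondary outcomes exploratory.

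**The concern.** A dropout allowance should leave the required number after the loss. Here 20% was added to 47, instead of 47 being divided by the 80% who remain. Under the plan's own dropout figure, the recruitment target therefore does not deliver the evaluable number on which its power statement rests.

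The effect is described in two ways that cannot both be right. The calculation defines 0.16 as the gap between the null and alternative flare rates in one RA cohort. The effect size entry calls it a gap between patients who flare and patients who do not. Flare is the outcome, so those two groups cannot differ by 16 points in flare rate. The bracketed subtractions start from 0.25, although the null rate is 0.26.

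At stake is the only quantitative justification of the sample size for the primary outcome, in a section that itself worries about being underpowered.

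**Working it through.** **Inputs** (all from View 2.11.1, item 2.0): P0 = 0.26; P1 = 0.10; two-sided exact test; alpha 0.05; n = 47; dropout 20%; recruitment 57.

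**1. Reproduce the plan's power.** Use an equal-tail exact binomial test. The lower limit L is the largest value with P(X <= L | n, 0.26) <= 0.025. The upper limit U is the smallest value with P(X >= U | n, 0.26) <= 0.025. Power = P(X <= L | n, P1) + P(X >= U | n, P1).

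| n | P1 | Alpha | Power | Plan's alpha | Plan's power |
|---|---|---|---|---|---|
| 47 | 0.10 | 0.0445 | 0.8143 | 0.0445 | 0.8143 |
| 109 | 0.15 | 0.0387 | 0.8036 | 0.0387 | 0.8036 |
| 394 | 0.20 | 0.0445 | 0.8017 | 0.0445 | 0.8017 |

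All three rows agree to four decimals. A minimum-likelihood two-sided test would give alpha 0.0486 at n = 109, not 0.0387. The equal-tail test is therefore the one the plan used.

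**2. Dropout arithmetic.**
- 47 x 1.20 = 56.4, rounded up to 57: the plan's figure.
- 57 x 0.80 = 45.6 evaluable.
- 47 / 0.80 = 58.75, rounded up to 59; 59 x 0.80 = 47.2 evaluable.
- 57 recruits leave 47 only if dropout is 1 - 47/57 = 17.5%.

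**3. Power at the number that remains (0.26 v 0.10).**

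| n | P(X <= 6) at 0.26 | Reject if | Alpha | Power |
|---|---|---|---|---|
| 45 | 0.0325 | X <= 5 or X >= 19 | 0.0256 | 70.8% |
| 46 | 0.0273 | X <= 5 or X >= 19 | 0.0272 | 69.0% |
| 47 | 0.0228 | X <= 6 or X >= 19 | 0.0445 | 81.4% |

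Below n = 47, P(X <= 6) exceeds 0.025, so the lower limit falls from 6 to 5. That step causes the drop.

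**4. How much is saw-tooth.** Power by the same test:
- n = 42 to 46: 76.0, 74.3, 72.6, 70.8, 69.0%.
- n = 47: 81.4%, a local peak.
- n = 48 to 51: 80.0, 78.5, 77.0, 75.5%.
- n = 52 to 61: at least 80% throughout (lowest 80.7%, at 56).

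A normal approximation moves only from 78.5% at 47 to 76.2% at 45 and 77.4% at 46. If the evaluable number is Binomial(M, 0.8), an added assumption, mean power is 74.1% for M = 57, 76.1% for M = 59 and 81.1% for M = 65.

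**5. Brackets.** 0.25-0.10 = 0.15, 0.25-0.15 = 0.10 and 0.25-0.20 = 0.05. With the table's null, 0.26-0.10 = 0.16, 0.26-0.15 = 0.11 and 0.26-0.20 = 0.06, which are the percentages printed. The null value matters: with P0 = 0.25, power at n = 47 would be 67.1%.

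**6. What 47 offers a flare versus non-flare comparison.** At a 26% rate, 47 x 0.26 = 12.2, so about 12 v 35. By the noncentral t distribution (two-sided alpha 0.05), 80% power needs a difference of about 0.96 SD. The plan gives no such calculation.

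**The case against.** **The loss is mostly discreteness.** The error is two recruits, and the test has more power at 42 than at 46. This stands. A reader might infer that the wrong inflation itself costs 11 to 12 points; under the Binomial assumption it costs about 2 (74.1% against 76.1%). The plan did choose an exact test, though, and quotes its power at one n, so the power it should report at the expected 45 to 46 is about 70%.

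**59 does not secure 80%.** This also stands. It gives 81.4% only at exactly 47 evaluable, and one to four more give 75.5% to 80.0%.

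**Dropout may come after week 6.** Participation lasts a year, flare is assessed within 6 weeks, and the plan does not time the dropout. More than 46 could therefore be evaluable for the primary outcome. But the plan itself applies the 20% to the 47 needed for that outcome, so on its own terms 57 falls short.

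**The per-group heading comes from the form.** This stands. The entry beneath it says the numbers are overall, and the plan assigns the two groups to the secondary outcome. A reader might infer that 47 are needed in each group; the documents do not support that. The separate sentence calling 16% a flare versus non-flare effect is the authors' own, and it is wrong.

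**Secondary outcomes are exploratory.** They are declared so, and no power calculation is owed for them. Nor would it be fair to compute power for 26% against 10% between flare and non-flare patients: that contrast exists only through the mislabelling. What remains is the statement that 57 is adequate for these outcomes, which nothing supports.

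**Estimation is hardly touched.** The first aim is to determine a rate. At 26%, the approximate 95% half-width, 1.96 x sqrt(0.26 x 0.74 / n), is 12.5 points at n = 47 and 12.8 at n = 45. This stands and limits the seriousness. The interim check of power that the section plans does not correct the figure.

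**Conclusion.** The point holds and should be fixed, but it is not critical. Under the stated 20% dropout, 57 recruits leave 45 to 46 evaluable RA patients. The plan's own equal-tail exact test then has 69% to 71% power against a 10% rate, below both the 80% target and the quoted 81%. The correct inflation gives 59. The 16, 11 and 6 points are one-sample differences from 0.26; the 0.25 in the brackets and the flare versus non-flare label are both errors.

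The 70% figure assumes that the 20% applies to the primary outcome, as the plan uses it, and that the test is the one that reproduces the plan's table. The maximum of 200 in Target Enrollment does not answer the point, because eligibility covers RA, OA and inflammatory arthritis; 57 is the only target tied to the primary outcome. A reader might infer that the study is fundamentally undersized, or that two more patients would restore it. The documents support neither: the shortfall is small, and power moves up and down with n over this range.

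**What to change.** In View 2.11.1, item 2.0:

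1. Either keep 57 and state about 45 to 46 evaluable RA patients with power of about 70%, or replace 57 with 59 RA patients and state that 81% holds only at exactly 47 evaluable. In both cases, give the power across the plausible evaluable range. If average power of 80% is wanted under random dropout, 65 recruits give 81.1% on the Binomial assumption.
2. Correct the brackets to 0.26-0.10, 0.26-0.15 and 0.26-0.20.
3. Describe the 16 points as a one-sample difference from the null rate of 0.26, and state that 47 is the total RA sample.
4. Remove the claim that 57 is adequate for the secondary outcomes. Optionally, note that about 12 v 35 patients gives 80% power only for a difference of about 0.96 SD.

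The cost is wording, plus either a lower stated power or two more recruits. Securing 80% on average would take about eight more (65 - 57). Each of these totals is below the maximum of 200, which is shared with OA and inflammatory arthritis patients.

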In aim 5 and 6 we will compare levels of serum and tissue biomarkers between RA who flare and RA who do not flare using T-tests or chi-square tests, as appropriate. We will correlate self-report functional scores and biomarkers with the development of flare using Spearman correlations.

After sequencing, the reads will be processed by the New York Genome Center in a dedicated RNA-Seq pipeline, consisting of ribosomal RNA filtering, genome mapping with STAR, various QC metrics obtained with picard tools and transcript quantification with HTSeq-count. The raw read counts will then be processed with one of the Bioconductor package for Differential Gene expression (DESeq, edgeR, or limma/voom).

[Help](#)

ID: 2014-233

View: 2.4 Consent Information

[Help](#)

Consent Information

1.0 Describe how, when, and where the consent process will be initiated:

If possible, before coming in to the hospital (either for a pre-operative visit or their surgery), patients will be called by a research team member to discuss the study and evaluate their interest in participating. Patients who are interested will then be consented prior to surgery by the study research assistant or their treating surgeon, or rheumatologist either in the office, in pre-surgical screening, or in the pre-op holding area. If convenient, patients can additionally review the study protocol with the coordinator over the phone, but they will always be consented in person. The consent will be placed in the patients' hospital chart.

In the event that a potential participant requires a translator and is scheduled to have surgery on a weekend, a co-investigator of the research study can contact the potential participant prior to the day of their surgery and consent the patient over the phone. The Hospital for Special Surgery's Language Services Phone Interpreter or in-house employee will translate the Informed Consent to Participate in a Research Study Involving Genetic Testing, the Short Form Consent, and the Research Authorization Form. The translator would function as the witness to the consenting process. If the participant agrees to enroll, the participant will sign these forms in person on the day of their first study visit.

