P1 is the value of the population proportion under the alternative hypothesis.

Summary Statements

A sample size of 47 achieves 81% power to detect a difference (P1-P0) of -0.1600 using a

two-sided binomial test. The target significance level is 0.0500. The actual significance level

achieved by this test is 0.0445. These results assume that the population proportion under the

null hypothesis is 0.2600.

Power Analysis of One Proportion

Chart Section

We are estimating the rate of the flare rate in RA post-arthroplasty based on previous data. However, if our estimates are wrong, we may be grossly underpowered. Therefore, an interim analysis is planned, when we have collected 25 RA patients to ensure we are adequately powered to detect the primary outcome of flare as previously defined.

- Alpha level: 0.05
- Beta or power level: 0.8 (80%)
- Primary outcome variable estimate (mean +/- s.d. for continuous outcome, frequency/percentage for categorical variable):

The primary outcome is rate of RA flare within 6 weeks of surgery. Since it's a rate, no mean and s.d. are available.

- Number of groups being compared (use 1 for paired analysis within the same subjects):

2 groups: RA – Flare vs. Non-Flare group for secondary outcome.

- Effect size or change expected between groups:

The expected effect size between the flare and non-flare group is 16%, but the interim analysis will be performed after we collect 50 patients.

- Resulting number per group:

First Name	Middle Name	Last Name	Title
[name]	MD
[name]	Research Assistant
[name]	Attending Physician

[Help](#)

ID: 2014-233

View: 3.0 IRB Application

[Help](#)

IRB Application

1.0 Please provide lay abstract:

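### The equal-variance t-test named for flare vs non-flare comparisons does not hold 5% at about 12 vs 35 patients if the group SDs differ; naming Welch's test is a cheap, minor improvement

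*Combined protocol and SAP*

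**What the plan says.** All references are to the Combined protocol and SAP, section 2.11.1.

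- **Data Analysis, under the primary-outcome heading.** The test for continuous variables is given as: "The two-tailed unpaired Student's t test, or Kruskal-Wallis tests will be performed to evaluate differences in continuous variables between groups". The groups are flare and non-flare. The rule for choosing is "depending on the distribution of the data, and the Scheffe or Bonferroni multiple comparisons test will be used for multiple comparisons". No variance check and no unequal-variance test is named anywhere.
- **Data Analysis, aim 4.** The patient VAS is to be analysed with a t-test or regression; the form of t-test is not stated.
- **Data Analysis, aims 5 and 6.** Serum and tissue biomarkers are compared "between RA who flare and RA who do not flare using T-tests or chi-square tests, as appropriate". Again the form is open.
- **Sample Size.** The two-sided 5% level, the 26% flare rate and the 47 evaluable patients are set here. The same part says that no mean or SD is available because the primary outcome is a rate.
- **Status.** The Data Analysis part declares all secondary outcomes exploratory.

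**The concern.** The pooled t-test tolerates unequal variances when the two groups are of similar size. It does not when one group is about three times the other, because the pooled variance is then dominated by the larger group. Here the imbalance is built into the plan by the expected flare rate.

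Equal spread cannot be taken for granted either. The groups are formed after surgery, by an outcome definition that uses DAS28 change or patient-reported worsening, and are then compared on related measures. If the flare group varies more, p-values are too small and intervals too narrow; if it varies less, the reverse.

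The stake is limited but real. The Background section says that the study will identify clinical and biologic candidates for further study as predictors of flare. These tests help to pick the candidates, and a miscalibrated test passes false ones or hides true ones.

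**Working it through.** **1. The plan's own figure.** Exact binomial test, N = 47, P0 = 0.26, P1 = 0.10, at most 0.025 in each tail: reject if X ≤ 6 or X ≥ 19.

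- Actual alpha = 0.0228 + 0.0217 = 0.0445.
- Power = P(X ≤ 6 | 0.10) + P(X ≥ 19 | 0.10) = 0.8143.

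Both match the Sample Size table. The rows for N = 109 and N = 394 also reproduce. The documents state no error rate for the t-test.

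**2. Group sizes.** 0.26 × 47 = 12.2 and 47 − 12.2 = 34.8, so about 12 vs 35. At the 10% alternative used for sizing, 0.10 × 47 = 4.7, so about 5 vs 42.

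**3. Why the pooled standard error goes wrong.** Set the non-flare SD to 1 and the flare SD to r.

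- Pooled: SE² = [(11r² + 34)/45] × (1/12 + 1/35)
- True: SE² = r²/12 + 1/35

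At r = 2: pooled (78/45) × 0.1119 = 0.1940; true 0.3333 + 0.0286 = 0.3619. The pooled SE is √(0.1940/0.3619) = 0.73 of the true one.

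At r = 0.5: pooled (36.75/45) × 0.1119 = 0.0914; true 0.0208 + 0.0286 = 0.0494. The pooled SE is √(0.0914/0.0494) = 1.36 times the true one.

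**4. Real type I error at a nominal two-sided 5%.** Simulation with normal data and equal means, 12 vs 35, 200,000 replicates (20,000 for Kruskal-Wallis). The SD ratios are assumptions.

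| SD ratio, flare/non-flare | Pooled t | Kruskal-Wallis | Welch |
|---|---|---|---|
| 0.5 | 0.9% | 2.0% | 5.0% |
| 0.67 | 1.9% | 2.9% | 5.0% |
| 0.8 | 3.0% | 3.5% | 5.1% |
| 1 | 5.0% | 5.0% | 5.1% |
| 1.25 | 7.8% | 6.4% | 5.1% |
| 1.5 | 10.5% | 7.9% | 5.0% |
| 2 | 15.1% | 9.6% | 5.1% |

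More patients do not cure it. At 52 vs 148 (26% of the 200 maximum, if all were RA) the pooled test still runs from 0.9% to 14.8% for ratios 0.5 to 2. At 5 vs 42 it runs from 0.2% to 24.4%, with Welch at 5.4% to 5.9%.

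**5. Which direction does the flare definition suggest?** As an illustration, suppose that flare were simply the top 26% of one normal change score. The cut is z = 0.643, with density 0.3244.

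- Variance above the cut: 1 + 0.643 × 1.248 − 1.248² = 0.246, where 1.248 = 0.3244/0.26.
- Variance below the cut: 1 − 0.643 × 0.438 − 0.438² = 0.526, where 0.438 = 0.3244/0.74.
- SD ratio: √(0.246/0.526) = 0.68, and the pooled test's error is about 2%, which is conservative.

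For a variable correlated 0.5 with that score, the ratio is √[(1 − 0.25 × 0.754)/(1 − 0.25 × 0.474)] = 0.96 and the error about 4.5%.

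**6. Price of Welch.** With equal SDs at 12 vs 35, power falls from about 0.648 to 0.621 for a standardised difference of 0.8, and from 0.833 to 0.808 for 1.0. On untransformed skewed data (exponential, or lognormal with sigma 1, the same in both groups), Welch's error is about 6% to 7% at 12 vs 35 and about 11% to 14% at 5 vs 42, whereas the pooled test stays between 4.4% and 5.6%.

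**The case against.** **The SD ratios are assumed.** This stands. The documents give no group SDs, and at equal SDs the pooled test is correct. A reader might infer from the flare definition that flarers vary more and that false positives are therefore inflated to 10% or 15%. The documents do not support that: selection by a threshold alone points the other way, to a ratio near 0.68, and close to 1 for moderately correlated variables. Flare can also be met through patient-reported worsening, so the truncation model is only an illustration. The direction stays unknown.

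**Not every comparison is affected.** This also stands. A reader might take the t-test to cover all continuous flare vs non-flare outcomes. In fact the plan gives effect sizes for the aim 2 domains, a generalised estimating equation for aim 3, regression as an option for the VAS, ANCOVA or GEE for change, logistic regression for HOOS and KOOS, and dedicated packages for the RNA-seq counts. The biomarker text ("using T-tests or chi-square tests, as appropriate") does not name Student's test and already allows Welch.

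**For variables that define flare, type I error is beside the point.** For DAS28 change or patient global, the means differ by construction, so error under equal means matters little. It matters for measures such as biomarkers, for which the documents give no reason to expect a large SD ratio.

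**Welch is not a cure-all.** Correct. Its hold on 5% is shown for roughly normal data, and the skewed-data figures above show where it fails.

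**What remains.** The plan names an equal-variance test at a ratio of about 1:3 with no provision for unequal spread. The listed alternative is triggered by distribution and drifts from 5% as well, and a Scheffe or Bonferroni step cannot repair miscalibrated p-values.

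**Conclusion.** The point holds conditionally and is minor. If the flare and non-flare SDs differ, the named test does not keep its 5% level at 12 vs 35: about 1% to 15% for SD ratios of 0.5 to 2, against about 2% to 10% for Kruskal-Wallis and about 5% for Welch with roughly normal data. These figures rest on the planned 26% flare rate, 47 evaluable patients, normal data and assumed SD ratios; the equal-variance reading rests on the name of the test. Neither the presence nor the direction of a distortion can be read from the documents.

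A reader might infer that the study's main result is at risk, because the sentence stands under the primary-outcome heading. It is not: the primary outcome is a single proportion, sized with an exact binomial test, and the affected comparisons are exploratory.

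**What to change.** In section 2.11.1, Data Analysis:

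- Replace Student's t-test with Welch's unequal-variance t-test for the flare vs non-flare comparisons of means.
- State that the t-tests in aim 4 (patient VAS) and in aims 5 and 6 (biomarkers) are Welch tests.
- Report each mean difference with its Welch confidence interval.
- Pre-specify a log transformation for positive, right-skewed biomarkers, reported as geometric-mean ratios, so that the test is not chosen after looking at the data. This changes the quantity estimated and does not suit scores that can be zero.
- If flarers turn out to be very few (about 5), present these comparisons as descriptive.

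The cost is a few phrases in the plan and no extra patients, visits or data. The price in performance is 2 to 3 points of power if the spreads are equal, and some inflation of Welch's error on skewed data left untransformed, mainly when flarers are very few.
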